6.4.3 End of Trial

During the End of Trial visit, subjects will complete the same questionnaires completed during the baseline visit. If the VAS score is < 50% of the VAS collected during the screening visit and is not using the two microdosing burst stimulation paradigms, the subject will exit the study. Subjects whose VAS score at the end of the trial is >50% of the VAS collected during the screening visit and is using one of the two microdosing burst stimulation paradigms, will be considered for permanent lead and IPG implantation.

The following assessments and information will be collected at the End of Trial visit:

- Clinical investigation specific examinations
 - Pain level as assessed by the VAS
 - Quality of life as assessed by the EQ-5D
 - Disability as assessed by the ODI
 - Anxiety and Depression as assessed by the HADS
 - Pain Catastrophizing as assessed by the PCS
 - Satisfaction as assessed by the PGIC
 - Medication usage;
 - Programming Form

Timing of visit	Activities at visit	Case Report Form
End of Trial	 Subject assess pain levels, quality of life, disability, anxiety, depression, pain catastrophizing, satisfaction, medication usage, and programming 	 VAS Form EQ-5D Form ODI Form HADS Form PCS Form PGIC Form Medication Usage Form Programming Form

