1.8 Study Assessments

Subjects will undergo a baseline assessment to collect primary and secondary outcome measures prior to the SCS trial. Specifically, baseline assessments will include: pain rating as assessed by the VAS, quality of life as assessed by EQ-5D, disability as assessed by ODI, anxiety and depression as assessed by the HADS, and pain catastrophizing as assessed by the PCS. Medication usage will also be collected during the baseline visit.

Subjects will be implanted with trial SCS system according to clinical practice and practitioner's discretion. At the end of the SCS trial period, subjects who experienced a reduction of 50% or more in average pain back and/or leg VAS scores with one of the two microdosing stimulation paradigms will be offered permanent implant and further participation in the study. The same primary and secondary outcomes measures will be collected at the end of the SCS trial period as well as at the 1, 3 and 6 months follow up visit, with the inclusion of patient satisfaction as assessed by the PGIC. Programming parameters will also be assessed during these visits.

2 Introduction

This document is a clinical investigation plan (CIP) for the BOLD clinical investigation. This clinical investigation is intended to evaluate the therapeutic efficacy of microdosing BurstDR[™] stimulation in

spinal cord stimulation (SCS) patients with chronic intractable back and/or leg pain. This clinical investigation is sponsored by Abbott.

This clinical investigation will be conducted in accordance with this CIP. All parties involved in the conduct of the clinical investigation will be qualified by education, training, or experience to perform their tasks and this training will be documented appropriately.

3 Background and Justification for Clinical Investigation

Spinal cord stimulation (SCS) is increasingly being used as an alternative for the treatment of chronic, intractable pain. In a systematic meta-analysis of the literature, Taylor et al. (2006) reported that SCS reduces pain, improves quality of life, reduces analgesic use, allows some patients to return to work and may also result in significant cost savings over time, while having minimally significant adverse events in patients with neuropathic back and/or leg pain.

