6.4.2 SCS Trial

During the trial implant phase, SCS leads will be implanted in the dorsal column based on physician discretion. According to standard clinical practices performed in the United States (US), the trial phase will last around 3-7 days. At the start of the trial phase, patients will be programmed with the first ON/OFF stimulation pattern (30 second STIM ON, 90 seconds STIM OFF). Patients who do not achieve adequate pain relief (at least 50% reduction in back and/or leg VAS from baseline) within the first 3-4 days will be reprogrammed to a new ON/OFF stimulation pattern (5 seconds ON/ 15 seconds OFF). Patients, who still do not achieve adequate pain relief within 2 to 3 days from reprogramming, will be reprogrammed to a continuous mode of BurstDR[™] stimulation and their trial evaluation will continue. These patients will be evaluated for an additional 2 days. At the end of the SCS trial, all subjects that experience at least 50% pain relief (according to average back and/or leg VAS) using one of the two microdosing burst stimulation paradigms will be considered further participation in the study. Patients who still do not achieve adequate

pain relief will be reprogrammed to a continuous mode of BurstDRTM stimulation and their trial evaluation will continue. These patients will be evaluated for an additional 2 days.

The following assessments and information will be collected at the SCS Trial visit

- Surgery Form
- Clinical investigation specific examinations
 - Programming Form

The following activities will be performed at the SCS Trial visit:

- SCS Trial Lead(s) Implant
- EPG Device programming

Timing of visit	Activities at visit	Case Report Form	
SCS Trial	SCS trial lead implant	Surgery Form	
	EPG programming	Programming Form	

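### Section 6.4.3 sets the End of Trial implant gate on the VAS score instead of the VAS reduction, so read literally it admits microdosing subjects with less than 50% relief

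*Combined protocol and SAP*

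**What the plan says.** Section 6.4.3 (End of Trial) contains two disposition sentences, both stated on the VAS score.

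- Implant: "Subjects whose VAS score at the end of the trial is >50% of the VAS collected during the screening visit", if on one of the microdosing patterns, are considered for permanent leads and an IPG.
- Exit: "If the VAS score is < 50% of the VAS collected during the screening visit", and the subject is not on a microdosing pattern, the subject leaves the study.

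The other sections state the gate on relief.

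- Section 6.4.2 takes forward "all subjects that experience at least 50% pain relief (according to average back and/or leg VAS", on either microdosing pattern. Sections 1.3, 5.1 and 6 repeat the same sentence. All four speak of further participation in the study.
- Section 1.8 speaks of permanent implant itself, and offers it to "subjects who experienced a reduction of 50% or more in average pain back and/or leg VAS scores" on either microdosing pattern.

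Sections 1.3, 5.1, 6 and 6.4.2 also define adequate relief as a VAS reduction from baseline of 50% or more, so a lower score is better.

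**The concern.** The implant sentence in 6.4.3 selects the opposite side of the threshold from the five other sections. It is the visit-level instruction for an invasive step, and three things depend on it.

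- **Who is implanted and followed.** The gate decides who supplies the 1, 3 and 6 month VAS values for the primary endpoint.
- **The post-implant target.** Sections 1.3, 5.1 and 6 define adequate relief after implant relative to the relief reached in the trial phase. A subject admitted at 25% relief would carry a 25% target into the search for the optimal program, which is a secondary endpoint in 5.3.2.
- **Deviations.** Section 9.1 defines a deviation as a failure to follow the protocol. Implanting a subject at 25% relief meets 6.4.3 and breaks 6.4.2, so the same act can be classified either way.

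**Working it through.** The plan has no figure to reproduce here. The check converts score to relief and compares the rules.

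**Inputs**
- Literal 6.4.3 implant rule: E > 0.50 × B and on microdosing, where E is the end-of-trial VAS and B the screening VAS.
- Rule in 1.3, 1.8, 5.1, 6 and 6.4.2: relief of at least 50% and on microdosing.
- Minimum baseline VAS: 6.0 cm on a 10.0 cm scale (5.4.1).
- Assumption: the screening VAS is the baseline VAS. The table in 6.4.1 labels that visit as both, and the schedule in 6.7 has only one VAS before the SCS trial.

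**Formula**

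Relief = (B − E) / B = 1 − E/B. Hence E/B > 0.50 is the same as relief < 50%, and E/B ≤ 0.50 is the same as relief ≥ 50%.

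**Microdosing subjects at B = 6.0 cm** (literal cut 0.50 × 6.0 = 3.0 cm)

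| E (cm) | Relief | Literal 6.4.3 | Other five sections |
|---|---|---|---|
| 4.5 | (6.0 − 4.5)/6.0 = 25% | considered for implant | does not qualify |
| 3.0 | (6.0 − 3.0)/6.0 = 50% | no instruction | qualifies |
| 2.25 | (6.0 − 2.25)/6.0 = 62.5% | no instruction | qualifies |

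The pattern does not depend on the baseline. At B = 10.0 cm the literal cut is 5.0 cm, and 6.0 cm (40% relief) is considered while 4.0 cm (60% relief) has no instruction.

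**The exit sentence**

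Read literally, it exits subjects who are not on microdosing and whose score is below 50% of screening, that is, who have more than 50% relief on continuous stimulation. The other sections imply that such subjects do not continue, because only microdosing responders go forward. The literal exit sentence is therefore compatible with them.

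**Would changing one word be enough?**

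Reading reduction for score in both sentences puts the implant threshold the right way round: 2.25 cm qualifies and 4.5 cm does not. Two points remain. The strict inequality still leaves out exactly 50% (3.0 cm), which the other sections admit. The exit sentence would then cover continuous-mode subjects with less than 50% relief, and 6.4.3 would no longer address continuous-mode responders. Both sentences are better rewritten than patched.

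**The case against.** The strongest reply is that this is an obvious slip with little consequence. Section 6.4.2, immediately before, gives the correct rule and the definition of adequate relief. Section 6.4.3 says only that subjects are considered for implant, and 6.4.4 leaves the implant to standard clinical practice, so no investigator is obliged to implant a non-responder. A microdosing non-responder should have been switched to continuous stimulation before the visit, and the microdosing condition in 6.4.3 then blocks implant even on the literal text. The study is a feasibility trial without formal hypotheses (7.1) or success criteria (7.6). All of this stands and limits the practical exposure. It does not remove the contradiction at the visit that gates surgery.

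It is also fair to say that the five other sections amount to two wordings, and that only 1.8 mentions permanent implant. The direction of the threshold is the same in both.

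Three stronger readings are tempting, and the documents do not support them.

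- **That many non-responders would still be on microdosing at the visit because the steps do not fit the trial.** The steps add up to 7 to 9 days (3 + 2 + 2 to 4 + 3 + 2), while 6.4.2 says "the trial phase will last around 3-7 days". But the length is approximate, and the section ties non-responders to the steps: their evaluation continues on continuous mode, and "These patients will be evaluated for an additional 2 days". A trial that simply stopped on day 3 or 4 would not follow the text. A subject who responds on microdosing and loses relief by the visit would meet the literal gate, but nothing in the documents says how often that happens.
- **That both sentences in 6.4.3 contradict the other sections.** Only the implant sentence clearly does.
- **That continuous-mode responders are given no disposition anywhere.** The literal exit sentence in 6.4.3 exits those with more than 50% relief. The question arises only if score is read as reduction.

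**Conclusion.** The point holds. The implant threshold in 6.4.3 is reversed: taken literally, it considers for implant microdosing subjects with less than 50% relief and gives no instruction in that section for microdosing subjects with 50% or more. It contradicts the relief rule for further participation in 1.3, 5.1, 6 and 6.4.2 and the reduction rule for permanent implant in 1.8. The likeliest explanation is that score was written where reduction was meant.

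The size is certain as text and small in expected practice. Every microdosing subject falls on the wrong side or outside the literal rule, but sites would probably notice, and no count of affected subjects can be derived. A reader should not infer that the protocol intends to implant non-responders. The conclusion assumes that the screening and baseline VAS are the same measurement. It does not rely on Figure 1, which is not shown in the text available; what that figure says about continuous-mode responders and trial length is for the sponsor to confirm. The wording should be corrected, but the matter does not call the design into question.

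**What to change.** Replace the implant sentence in 6.4.3 with one on the reduction, for example: *A subject whose average back and/or leg VAS has fallen by at least 50% from baseline while on either microdosing pattern will be considered for implantation of permanent leads and an IPG.* This also admits exactly 50%, as the other sections do.

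Align the exit sentence: *A subject who does not meet this criterion once the reprogramming steps in 6.4.2 are complete will exit the study.* This second sentence is an inference from the other sections. The sponsor should confirm against Figure 1 that it is meant to include subjects who respond only on continuous stimulation, and can state at the same time whether the trial may run beyond 7 days so that the steps can finish.

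The cost is a one-paragraph amendment, a clarification to sites and the check against Figure 1. The threshold correction needs no additional patients, visits or procedures.

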6.4.4 Permanent Implant

Permanent implant will be performed according to standard clinical practice.

The following assessments and information will be collected at the Permanent Implant visit

Surgery Form

The following activities will be performed at the Permanent Implant visit:

- SCS Permanent Lead(s) Implant
- IPG Implant

Timing of visit	Activities at visit	Case Report Form
SCS Permanent	SCS permanent lead implant	Surgery Form
Implant	IPG implant	

6.4.5 Activation

IPG will be programmed using burst stimulation according to standard programming techniques.

The following assessments and information will be collected at the Activation visit

- Clinical investigation specific examinations
 - Programming Form

e Report Form
mming Form
1

6.4.6 Scheduled Follow-ups

Subjects will be followed up for 6 months post-activation visit with follow-up assessments at 1, 3 and 6 months. During each visit, subjects will complete the same questionnaires completed during the end of trial visit.

The following assessments and information will be collected at the End of Trial visit:

- Clinical investigation specific examinations
 - Pain level as assessed by the VAS
 - Quality of life as assessed by the EQ-5D
 - Disability as assessed by the ODI
 - Anxiety and Depression as assessed by the HADS
 - Pain Catastrophizing as assessed by the PCS
 - Satisfaction as assessed by the PGIC
 - Medication usage;
 - Programming Form

Timing of visit	Activities at visit	Case Report Form
End of Trial	Subject assess pain levels, quality of life, disability, anxiety, depression, pain catastrophizing, satisfaction, medication usage, and programming	 VAS Form EQ-5D Form ODI Form HADS Form PCS Form PGIC Form Medication Usage Form Programming Form

This confidential document is the property of Abbott and shall not be reproduced, distributed, disclosed or used without the express written consent of Abbott.

6.5 Patient Reported Outcome (PRO) Measures

The Study Coordinator or designee will administer patient-reported outcome questionnaires. It is important the subject understands the meaning of all words and instructions in the questionnaires. The subject should be instructed to ask any questions about the questionnaires if further explanation is needed. Once the questionnaires are completed, the Study Coordinator or designee will review for completeness to verify that all questions have been answered according to the directions provided.

The following PRO measures will be collected according to the study requirements.

- Pain level as assessed by the VAS
- Quality of life as assessed by the EQ-5D
- Disability as assessed by the ODI
- Pain Catastrophizing as assessed by the PCS
- Anxiety and Depression as assessed by the HADS

6.6 Unscheduled Visits

[figure not shown]
An Unscheduled Visit is defined as any visit where an active study subject returns to the participating study site for medical care outside of a specified study visit. Unscheduled visits may include subjects returning to the office for an adverse event. The visit should be documented by completing the Unscheduled Visit Form and any other applicable forms (Adverse Event, Deviation, Death and/or Withdrawal Form.

6.7 Study Flow Chart

The Study Flow Chart and the Table 2 below summarize subject flow and requirements of this clinical investigation.

Figure 1: Study Flow Chart

Visit	Enrollment	Baseline	SCS Trial	End of Trial	SCS Implant	Activation	Follow-up Visits*
Study Activity							
Informed Consent Process	х						
Inclusion/Exclusion Criteria Screening	х						
VAS Assessment		X		Х			Х
Enrollment Form	Х						
EQ-5D Assessment		X		X			Х
ODI Assessment		X		Х			Х
HADS Assessment		X		X			Х
PCS Assessment		X		X			Х
PGIC Assessment				X			Х
Trial System Implant			х				
Permanent System Implant					x	x	
Adverse Event	(X)	(X)	(X)	(X)	(X)	(X)	(X)
Deviation	(X)	(X)	(X)	(X)	(X)	(X)	(X)
Termination	(X)	(X)	(X)	(X)	(X)	(X)	(X)
Death	(X)	(X)	(X)	(X)	(X)	(X)	(X)

Table 2: List of all clinical investigation specific tests and procedures

(X) If applicable

* Follow up visit assessments will be performed at months $1(30 \pm 21 \text{ days})$, $3(90 \pm 21 \text{ days})$ and $(180 \pm 21 \text{ days})$

6.8 Description of Activities Performed by Sponsor Representatives

Trained sponsor personnel may perform certain activities to ensure compliance to the clinical investigational plan and may provide technical expertise.

Sponsor personnel may:

• Provide technical support to the Investigators during trial

Sponsor personnel will not:

- Perform the informed consent process
- Provide medical diagnosis or treatment to subjects
- Discuss a subject's condition or treatment with a subject without the approval and presence of a health care practitioner
- Independently collect clinical investigational data

While Sponsor representatives may perform these activities, the Principal Investigator remains responsible for ensuring all clinical investigation data is collected as required per CIP.

6.9 Subject Study Completion

Subject participation in the clinical investigation will conclude upon completion of the 6-month visit. Upon completion of subject participation in the clinical investigation, the subject will return to standard of care.

6.10 Subject Withdrawal

Subjects must be informed about their right to withdraw from the clinical investigation at any time and for any reason without sanction, penalty or loss of benefits to which the subject is otherwise entitled. Withdrawal from the clinical investigation will not jeopardize their future medical care or relationship with the investigator. Subjects will be requested to specify the reason for the request to withdraw. The investigator must make all reasonable efforts to retain the subject in the clinical investigation until completion of the clinical investigation.

The investigator may decide to withdraw a subject from the study at any time with reasonable rationale. The subject's future care will not be influenced by a decision, voluntary or otherwise, to withdraw from the study. All reasonable efforts should be made to retain the subject in the clinical study until completion of the study.

Reasons for subject's withdrawal include, but are not limited to:

- Subject refuses to continue participating in the study
- Subject does not meet the inclusion/exclusion criteria and does not require additional follow-up for safety reasons.
- Subject is deceased (cause must be documented)
- Subject's non-compliance
- Subject's participation is terminated by the PI or investigator, although the subject consented, since participation is no longer medically appropriate
- Subject is 'lost to follow up': Subject does not adhere to the scheduled follow up visits but has not explicitly requested to be withdrawn from the clinical study. (This does not apply to missed visits). Site personnel should at all times make all reasonable efforts to locate and communicate with the subject in order to achieve subject compliance to the scheduled follow up visits:
 - A subject will be considered 'Lost to Follow Up' after a minimum of 2 phone calls of a physician or delegate at the investigational site to the subject or contact. These 2 phone calls need to be documented in the subject's hospital records.
 - If these attempts are unsuccessful, a letter should be sent to the subject's last known address or general practitioner (GP) and a copy of this letter should be maintained in the subject's hospital records.

Note: If a subject misses one or more of the scheduled follow up visits (inclusive of the assigned visit windows), this will be considered as a missed visit. The subject may therefore still return for subsequent visits and will not be excluded from the study.

If a subject withdraws from the clinical study, the site will record the subject's reasons for withdrawal, on a Withdrawal CRF.

When subject withdrawal from the clinical study is due to an adverse event the subject will be followed until resolution of that adverse event or determination that the subject's condition is stable. The status of the subject's condition should be documented at the time of withdrawal.

The third follow up visit will be the final study visit. The subject will complete the questionnaires as in the previous follow up visit and will exit the study.

7 Statistical Considerations

The following section describes the statistical methods for the clinical investigation and justification of the design. Additional details on statistical analyses, including sensitivity analyses, poolability analyses, subgroup analyses and analysis of descriptive endpoint(s) may be maintained in a separate Statistical Analysis Plan (SAP).

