1.7 Enrollment

A patient becomes a subject once he/she has been fully informed about the study, has agreed to participate, signed & dated the consent.

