6.2 Screening

Potential patients presenting at the investigational sites will be fully informed about the clinical investigation, following the established Informed Consent process (described in section 6.1). Once a duly dated and signed Informed Consent Form is obtained, the screening procedures may begin.

Records of patients who are screened must be maintained.

In case the subject does not meet all inclusion criteria or meets any of the exclusion criteria, the subject is considered a screening failure. The Principal Investigator or the delegated study personnel will record the screening failure in the hospital records and on a screening log as required.

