6.3 Point of Enrollment

Subject is considered enrolled in the clinical investigation from the moment the subject has provided a written Informed Consent and has been confirmed to meet all inclusion criteria and none of the exclusion criteria.

The Principal Investigator or delegated study personnel will record enrollment information (name of the clinical investigation, date of consent and Inclusion/exclusion information) in the hospital records and complete and submit an applicable CRF in a timely manner.

Notification of enrollment to the Sponsor is considered to have occurred when the Sponsor has received the applicable CRF.

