9.1 Deviations from CIP

A deviation is defined as an instance(s) of failure to follow, intentionally or unintentionally, the requirements of the CIP. The investigator should not deviate from the CIP.

In some cases, failure to comply with the CIP may be considered failure to protect the rights, safety and well-being of subjects; such non-compliance exposes subjects to unreasonable risks. Examples: failure to adhere to the inclusion/exclusion criteria, failure to perform safety assessments intended to detect adverse events. Investigators should seek to minimize such risks by adhering to the CIP.

The PI must maintain accurate, complete, and current records, including documents showing the date of and reason for each deviation from the CIP. Relevant information for each deviation will be documented as soon as possible on the applicable CRF. The site will submit the CRF to the Sponsor.

The PI is required to adhere to local regulatory requirements for reporting deviations to IRB/EC.

Under emergency circumstances, deviations from the CIP to protect the rights, safety and well-being of subjects may proceed without prior approval of the Sponsor and the IRB/EC. Such deviations shall be documented and reported to the Sponsor and the IRB/EC as soon as possible.

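### Section 6.10 allows withdrawal for not meeting the entry criteria with no time limit, so follow-up VAS can be lost after lead insertion in an open-label study that names no analysis set

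*Combined protocol and SAP*

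**What the plan says.** - **Withdrawal reason (6.10).** The list includes "Subject does not meet the inclusion/exclusion criteria and does not require additional follow-up for safety reasons". No time point is attached, the list is expressly not exhaustive, and the subject's non-compliance is a separate entry.
- **Investigator's power (6.10).** "The investigator may decide to withdraw a subject from the study at any time with reasonable rationale".
- **Retention duty (6.10).** "All reasonable efforts should be made to retain the subject in the clinical study until completion of the study". A similar sentence appears in the section's opening paragraph, and a missed visit does not exclude a subject.
- **Screening (6.2).** A consented person who fails the criteria is dealt with there: "the subject is considered a screening failure".
- **Enrollment (6.3).** Enrollment requires written consent and that the subject "has been confirmed to meet all inclusion criteria and none of the exclusion criteria".
- **Who is a subject (1.7).** "A patient becomes a subject once he/she has been fully informed about the study, has agreed to participate, signed & dated the consent".
- **Deviations (9.1).** An example of serious non-compliance with the plan is "failure to adhere to the inclusion/exclusion criteria". Deviations are documented on a CRF. The section does not say whether the subject stays in or leaves.
- **Analysis (7.1.1.1, 7.1.1.3).** VAS is analysed by repeated measures ANOVA. Missing data are reported by visit and outcome and are not imputed. No analysis set is named.
- **Safety (9.2, 6.10).** Surveillance ends at withdrawal; when an adverse event caused the withdrawal, 6.10 follows the subject until resolution or stability.

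**The concern.** Once eligibility has been confirmed and leads are in place, ending follow-up on eligibility grounds is a decision taken after exposure. The study is open label with a single treatment path, so whoever takes that decision may already know how the subject's pain has responded. If the decision is related to the response, the subjects who remain are a selected group.

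The primary endpoint is the change in VAS from baseline through the SCS trial to long-term follow-up, with no control group against which such selection could be seen. Section 7.1 says that the results may feed a later study with formal hypothesis testing, so a flattered estimate could be carried forward. Later safety observation would also be lost for those withdrawn for reasons other than an adverse event.

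**Working it through.** The plan gives no figure to reproduce on this point: there is no sample size calculation, no expected number implanted and no withdrawal rate.

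**1. When can the reason apply?** Sections 6.2 and 6.3 together deal with ineligibility found before enrollment. If the entry in 6.10 meant only that, it would add little. It also refers to a need for safety follow-up, and under 9.2 safety surveillance begins only with the procedure. Its natural reach therefore includes subjects already exposed.

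**2. Does the safety clause exclude implanted subjects?** It takes out those who need safety follow-up. Nothing says that an implant in itself creates that need, and 6.9 returns completers, who carry implants, to standard care after month 6. The clause narrows the reason without closing it.

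**3. What is lost on withdrawal?** The flow chart (6.7) schedules VAS at five points: baseline, end of trial, and months 1, 3 and 6.

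| Withdrawn after | VAS already recorded | VAS never collected | VAS used if the ANOVA is complete-case |
|---|---|---|---|
| Lead insertion, before end of trial | 1 | 4 | 0 |
| End of trial | 2 | 3 | 0 |
| Month 1 | 3 | 2 | 0 |
| Month 3 | 4 | 1 | 0 |
| Month 6 | 5 | 0 | 5 |

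The third column follows from the visit schedule. The fourth is conditional: the plan does not say how incomplete subjects enter the ANOVA.

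**4. How large could the effect be?** Both illustrations use assumed inputs.

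(a) If k of n subjects contribute no VAS, the reported mean exceeds the mean of all n by (k/n) × (mean fall in those kept − mean fall in those lost). Assume n = 40, a fall of 4 cm in those kept and 1 cm in those lost.
- k = 4: the mean over all is (36×4 + 4×1)/40 = 3.7 cm against 4.0 cm reported, a shift of 0.10 × 3 = 0.3 cm.
- k = 8: (32×4 + 8×1)/40 = 3.4 cm against 4.0 cm, a shift of 0.20 × 3 = 0.6 cm.

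(b) Assume normally distributed changes and that exactly the worst k responders leave the analysis (simulation, 100,000 draws). Shift in mean improvement, in SD of the change:

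| n analysed (assumed) | k = 1 | k = 2 | k = 3 |
|---|---|---|---|
| 30 | 0.071 | 0.132 | 0.187 |
| 40 | 0.056 | 0.103 | 0.147 |
| 60 | 0.039 | 0.073 | 0.105 |

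For a few subjects the shift is modest. It favours benefit only because poor responders were assumed to be the ones lost.

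**The case against.** The case on the other side is substantial.

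- **Screening-failure reading.** Section 1.7 makes a person a subject at consent, and 6.2 uses the word in that sense: "In case the subject does not meet all inclusion criteria or meets any of the exclusion criteria, the subject is considered a screening failure". The 6.10 entry could be meant for the same people. This reading is possible, but it leaves the entry nearly redundant and its safety clause hard to explain.
- **No deletion of data.** A reader might infer that implanted subjects are taken out of the data once their pain result is known. The documents do not say so. Withdrawal ends participation and its reason goes on a Withdrawal CRF; scores already collected are not stated to be excluded. What is certain is the loss of later scores. Loss of earlier ones depends on how the ANOVA is run.
- **Medication increase.** A reader might also infer that a subject who relapses and takes more analgesic ceases to be eligible. The criterion in 5.4.1 is willingness, at entry, to hold medication without an increase until month 3, so a later increase does not make it unmet. Medication change is itself a secondary endpoint, and Section 6 directs inadequate relief to reprogramming. What stands is that such an increase could be handled as non-compliance, which has no time limit either.
- **Deviation rule.** Section 9.1 is silent on removal, so it does not contradict 6.10. A deviation can be recorded and the subject also withdrawn. The gap is that no section says which course applies.
- **Feasibility setting.** There is no formal hypothesis (7.1) and no success criterion (7.6), and Section 7 allows sensitivity analyses to sit in a separate SAP. This lowers the weight of the point but does not answer it.

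**Conclusion.** The point holds in a limited form. Section 6.10 permits avoidable loss of follow-up after lead insertion, on grounds of eligibility or non-compliance, by an investigator who can know the VAS. The safety clause and the retention duty reduce the scope for this without removing it. Later VAS is then not collected or imputed, and the plan does not say how the subject is analysed.

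The claim that the month 1 to 6 result *is* biased towards benefit goes further than the documents allow. They give no number implanted, no rate of such withdrawals and no link between withdrawal and response. Bias towards benefit requires that poor responders are the ones lost. The illustrated sizes (0.3 to 0.6 cm under one set of assumptions; 0.04 to 0.19 SD for one to three worst responders among 30 to 60) show what could happen and are not estimates. Severity is minor to moderate.

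**What to change.** In 6.10:

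1. Limit the eligibility reason to the period before trial lead insertion.
2. After that, record an eligibility breach or protocol non-compliance (including a medication increase) as a deviation under 9.1, and continue scheduled data collection unless the subject withdraws consent. Treatment decisions stay with the investigator.

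In 7.1.1:

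3. State that all data up to any withdrawal are kept and that the VAS analysis includes these subjects. For this to be true, the repeated measures analysis must accept incomplete records. A mixed model for repeated measures does so without imputation and so fits 7.1.1.3.
4. Add one sensitivity analysis excluding eligibility breaches.

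It would also help to align 1.7 with 6.3 on when a person is a subject and when enrolled.

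The cost is a short amendment, one extra table and the remaining visits of a few subjects. The downside is that a few ineligible subjects stay in the primary analysis, which the sensitivity analysis makes visible. The investigator's general power to withdraw a subject remains; item 3 limits its effect on data already collected but does not recover visits that never take place.
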